13.3 Reporting to FDA

- Serious adverse events will be forwarded to FDA by the IND MD Anderson (Safety Project Manager IND Office) according to 21 CFR 312.32.

It is the responsibility of the PI and the research team to ensure serious adverse events are reported according to the Code of Federal Regulations, Good Clinical Practices, the protocol guidelines, the sponsor's guidelines, and Institutional Review Board policy.

Investigator Communication with Supporting Companies:

13.4 For Comparator Drugs/Secondary Suspects (Concomitant Medications), all serious adverse experiences will be forwarded to the product manufacturer by the investigator.

13.5 Pregnancies

Any pregnancy that occurs during study participation should be reported. The pregnancy should be followed up to determine outcome, including spontaneous or voluntary termination, details of the birth, and the presence or absence of any birth defects, congenital abnormalities, or maternal and/or newborn complications.

13.6 Long Term Extension Phase

Patients will continue to be assessed for serious adverse events in the long term extension. Routine and expected AEs will not be collected in the case report form. Reporting of events to sponsor and supporter will remain as above.

14.0 STATISTICAL CONSIDERATIONS / DATA ANALYSIS

14.1 Phase I-II Dose-Finding Design

This is a phase I-II dose-finding trial to determine the optimal dose of the targeted oral agent MGCD516 when combined with immunotherapy via Nivolumab at fixed dose 240 mg IV every 2 weeks, in patients with metastatic renal cell carcinoma with clear cell component who have had prior treatment with anti-VEGF agents. The scientific goal of the trial is to determine an optimal MGCD516 dose level among the four levels **60, 80, 120, 150** mg/day given orally each day until toxicity of progressive disease. Dose-finding will be done using the sequentially adaptive phase I-II late-onset EffTox (Lo-EffTox) trade-off-based design of Jin et al.⁶⁰⁻⁶² For the goal of determining an optimum dose, dose limiting Toxicity within 12 weeks from the start of therapy is defined as described in section 5.3, and Efficacy is defined as achieving CR, PR, or stable disease within 6 weeks. Patients who have received at least 6 infusions of nivolumab 240 mg IV every 2 weeks with no DLTs related to nivolumab, will have the option to transition to the equivalent nivolumab schedule of 480 mg IV every 4 weeks. Because such a change will occur after at least 12 weeks from study initiation the endpoints are not affected for the purpose of dose escalation and de-escalation.

[figure not shown]
Each cohort will include no more or less than 3 patients. A maximum of 60 patients will be treated in up to 20 cohorts of size 3, with the first cohort treated at **80** mg/day, all successive

Proprietary of MD Anderson Cancer Center

doses chosen by the Lo-EffTox method, and no untried dose level skipped when escalating. Enrollment will continue without delay except, we also require at least one patient's toxicity outcome to have been observed at the current dose (which takes a maximum of 12 weeks) before enrolling the next cohort of patients. For the two Lo-EffTox dose acceptability rules, the upper limit on the probability of toxicity is .40, the minimum probability of Efficacy .50, and cut-offs .10 will be used for both stopping probability criteria. If the lowest dose level is found to be unacceptable in terms of either high toxicity or low efficacy, the trial will be terminated and no dose level will be selected. The three equivalent trade-off probability pairs used for computing the trade-off contours are (.50, 0), (.70, .25), (1, .65). The prior hyper-parameters were computed based on the assumed prior means $\text{Prob}(\text{Efficacy} | \text{dose}) = .25, .30, .35, .50$ and $\text{Prob}(\text{Toxicity} | \text{dose}) = .20, .25, .30, .40$, respectively, at the four MGCD-516 dose levels. The overall prior effective sample size = 1.

The Lo-EffTox design will be implemented using the specialized computer program developed by Jin et al.⁶⁰ The study biostatistician [name], [name], or [name] in the Biostatistics Department should be consulted as necessary during trial conduct. Secondary outcomes will include progression-free survival (PFS) time, overall survival (OS) time, objective response rate (ORR), and quality of life (QOL). Unadjusted distributions of the time-to-event outcomes will be estimated using the method of Kaplan and Meier⁶⁸ and their relationship to prognostic covariates will be evaluated by Bayesian piecewise exponential survival regression.⁶⁹

A Toxicity/Efficacy Summary will be submitted to IND Office Medical Monitor; every three patients, after the first twelve weeks of study therapy or administration is discontinued, whichever comes first, until 60 patients have completed study therapy.

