3.4 Updated results from the present protocol

From May 2017 through February 2020, 42 patients were enrolled in the present trial. At data cutoff (September 21, 2020), 12/42 patients (28.6%) continued to receive trial treatment. The median follow-up time was 18.7 months (95% CI 13.5 to 24.3). Sitravatinib (MGCD516) starting doses of 60, 80, 120, and 150 mg daily were selected according to the late-onset efficacy-toxicity (LO-EffTox) design for 0, 15 (35.7%), 24 (57.1%), and 3 (7.1%) patients. Overall, regardless of sitravatinib starting dose, the combination of sitravatinib plus nivolumab yielded an objective response rate (ORR) of 35.7% (15/42 patients) and a disease control rate (DCR) of 88.1% (37/42 patients). Complete response was noted in one patient (2.4%), who received a sitravatinib starting dose of 80 mg. The posterior mean for the median progression free survival (PFS) was 11.7 months [95% credible interval (CrI) 8.2 to 16.6]. Median overall survival (OS) was not reached, and 34/42 patients (80.1%) were alive at the time of data cutoff. Because we designed our trial to reflect the patient population enrolled in the CheckMate 025 phase III trial of nivolumab monotherapy in advanced ccRCC, we performed historical comparisons with CheckMate 025 using conservative Bayesian non-informative priors. Combining the three sitravatinib dose groups, the posterior probabilities that sitravatinib plus nivolumab yielded higher ORR and longer PFS than those reported for nivolumab monotherapy in CheckMate 025 were 96% and 100%, respectively.

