Dose-limiting toxicities (DLTs) were noted in all three patients treated with 150 mg daily. The 120 mg dose produced an ORR of 37.5% (9/24 patients) compared with the ORR of 26.7% (4/15 patients) observed with 80 mg. The 80 mg dose was associated with fewer DLTs (4/15 patients; 26.7%) compared with the 120 mg dose (10/24 patients; 41.7%). The estimated EffTox desirability scores were 0.622, 0.787, 0.755, and 0.630 for the 60, 80, 120, and 150 mg doses, respectively. Because the 80 and 120 mg doses had nearly identical estimated trade-off desirability scores, we compared them using additional criteria. The Bayesian posterior probabilities of sitravatinib 120 mg producing a higher ORR and longer PFS, compared with 80 mg were 80.7% and 68.3% respectively. The posterior probabilities of sitravatinib 120 mg yielding lower level of depression, higher quality of life, and higher hope for the future scores at 3 months compared with sitravatinib 80 mg were 92.7%, 82.6%, and 90.5%, respectively. Thus, all metrics favored the sitravatinib

Proprietary of MD Anderson Cancer Center

starting dose of 120 mg.

Adverse events (AEs) requiring dose reduction of sitravatinib throughout the treatment course were noted in 22/42 patients (52.4%). The primary reason for treatment discontinuation was disease progression (25/42 patients [59.5%]). Treatment discontinuation due to AEs was noted in 4/42 patients (9.5%). Death due to toxicity occurred in one patient who developed respiratory failure from myasthenia gravis. High-dose glucocorticoids (prednisone \geq 40 mg/day or equivalent) for the management of immune-related AEs were administered in 8/42 patients (19%). Additional immunosuppressive strategies such as infliximab were needed in 2/42 patients (4.8%).

In conclusion, this is the first study to evaluate the safety and efficacy of sitravatinib (MGCD516) plus nivolumab in ccRCC. Higher ORR and longer PFS with sitravatinib plus nivolumab in patients with ccRCC that progressed on prior antiangiogenic therapies were seen, compared to historical studies with nivolumab or TKI monotherapies in this setting. Furthermore, we found that the sitravatinib starting dose of 120 mg demonstrated the optimal tradeoff between efficacy, toxicity, and quality of life. The present trial provided a strong rationale for larger ongoing clinical trials utilizing sitravatinib 120 mg in combination with anti-PD1 therapy across multiple tumor types.

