14.2 Design Operating Characteristics

Operating characteristics of the design are summarized below, based on simulations with 1000 replications per scenario. In the simulations, it is assumed that the times to toxicity and efficacy follow Weibull distributions, the percentage of toxicity (or efficacy) events occurring in the later half of each evaluation interval is 50%, and the accrual rate is 2 cohorts per month.

Scenario		Dose (mg/day)					
		60	80	120	150	None	
1							
	True pT, pE	.20, .25	.30, .45	.40, .70	.50, .95	-	
	Trade-off Value	-0.83	-0.58	-0.24	0.12	-	
	% selected	0	11.5	41.0	41.0	6.5	
	# Patients Treated	3.5	8.7	18.8	27.6	-	
2							
	True pT, pE	.20, .40	.30, .65	.60, .70	.90, .75	-	
	Trade-off Value	-0.53	-0.18	-0.55	-0.91	-	
	% selected	8.4	75.5	1.4	0	14.7	
	# Patients Treated	8.0	31.1	10.6	6.2	-	
3							
	True pT, pE	.30, .65	.60, .72	.65, .75	.70, .78	-	
	Trade-off Value	-0.18	-0.51	-0.52	-0.54	-	
	% selected	78.4	10.3	0.1	0	11.2	
	# Patients Treated	27.5	18.5	6.8	3.9	-	
4							
	True pT, pE	.10, .15	.15, .20	.20, .25	.25, .30	-	
	Trade-off Value	-0.87	-0.85	-0.83	-0.81	-	
	% selected	0	0	0	3.8	96.2	
	# Patients Treated	3.2	3.3	4.3	22.2	-	
5							
	True pT, pE	.50, .25	.60, .35	.70, .45	.80, .56	-	
	Trade-off Value	-1.30	-1.26	-1.21	-1.14	-	

% selected	0	0	0	0	100
# Patients Treated	4.2	6.2	4.9	5.4	-

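### Section 14.1 ends the whole trial for low efficacy at the lowest dose alone, which can discard an acceptable higher dose; the printed operating characteristics look incompatible with that sentence

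*Combined protocol and SAP*

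**What the plan says.** Section 14.1 sets two dose acceptability criteria: "the upper limit on the probability of toxicity is .40, the minimum probability of Efficacy .50". Each is judged against a posterior probability cut-off of .10. A trial-level rule follows: "If the lowest dose level is found to be unacceptable in terms of either high toxicity or low efficacy, the trial will be terminated". The consequence is spelled out: "the trial will be terminated and no dose level will be selected". No other trial-level stopping rule appears. Sections 5.3 and 6.2.2 repeat the allocation method without one.

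The same section gives prior means for efficacy of .25, .30, .35 and .50, and for toxicity of .20, .25, .30 and .40, at 60, 80, 120 and 150 mg. The first cohort starts at 80 mg, the second level.

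Section 14.2 then reports: "Operating characteristics of the design are summarized below, based on simulations with 1000 replications per scenario". It does not say which termination rule was simulated. Section 3.4 reports the starting doses actually used at the four levels: "were selected according to the late-onset efficacy-toxicity (LO-EffTox) design for 0, 15 (35.7%), 24 (57.1%), and 3 (7.1%) patients".

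**The concern.** The sentence treats toxicity and efficacy alike, but they do not support the same inference. If the lowest dose is too toxic and toxicity rises with dose, every dose is too toxic, and stopping is logical. If the lowest dose is not effective enough and efficacy rises with dose, as the plan's own priors assume, the higher doses are the ones still worth studying.

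Two things are at stake. First, a trial run to the letter could end with no dose selected while a higher dose meets both criteria. Second, the table in Section 14.2 shows trials running close to full size and selecting higher doses when 60 mg is truly below the efficacy floor. If the table was produced under a different rule, its selection and no-dose probabilities do not describe the design as written.

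The sentence also leaves open whether 60 mg must be tried before it can be judged. With a start at 80 mg this matters, because a model-based verdict on 60 mg is available without any patient treated there.

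**Working it through.** **Inputs.** From Section 14.1: limits .40 (toxicity) and .50 (efficacy), cut-offs .10, contour points (.50, 0), (.70, .25), (1, .65), the prior means above, prior effective sample size 1, cohorts of 3, maximum 60, start at 80 mg, no untried level skipped upward. From Section 14.2: true rates, percentages selected, patients treated, and accrual of 2 cohorts per month.

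**Step 1: reproduce the printed trade-off values.** The contour gives

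value = 1 − {[(1 − pE)/.50]^p + (pT/.65)^p}^(1/p).

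Solving (.30/.50)^p + (.25/.65)^p = 1 gives p = 0.977. For Scenario 2 at 80 mg: .70^p = .706, (.30/.65)^p = .470, sum 1.175, and 1 − 1.175^(1/p) = −0.18, as printed. All 20 printed values reproduce to two decimals. This validates the contour and the scenario inputs, not the stopping logic.

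**Step 2: which doses truly meet the limits.**

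- Scenario 1: 60 mg has efficacy .25, below the floor. 120 mg has toxicity exactly .40 and 150 mg has .50, so this scenario serves only as evidence of inconsistency.
- Scenario 2: 60 mg has efficacy .40, below the floor. 80 mg (.30, .65) is clearly acceptable.
- Scenario 4: 60 mg has efficacy .15. No dose reaches .50, so selecting none is correct; the informative figure is how far the trial escalates first.

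Printed patient totals: Scenario 1, 3.5 + 8.7 + 18.8 + 27.6 = 58.6; Scenario 2, 8.0 + 31.1 + 10.6 + 6.2 = 55.9; Scenario 4, 3.2 + 3.3 + 4.3 + 22.2 = 33.0.

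**Step 3: hand check.** Use 60 mg data alone with an assumed Beta(.25, .75) prior (mean .25, weight of one patient). After 0/3 the posterior is Beta(.25, 3.75) and Pr(pE > .50) = .011, below .10. After 1/3 it is .198, above .10. One cohort at 60 mg would therefore trigger termination with probability .75³ = 42% in Scenario 1 and .60³ = 22% in Scenario 2. The real model borrows across doses, so this shows only how easily the trigger fires.

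**Step 4: simulate three readings of the rule.** The hyper-parameters are not printed, so they were assumed. Three separately written approximate simulators were used:

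- **I:** quadratic logistic efficacy and linear logistic toxicity in centred log dose; three priors fitted to effective sample size about 1; immediate outcomes (1000 runs per cell) and a late-onset approximation (500 runs per cell).
- **II:** the same model forms on a grid; three prior splits; no delay, or the last 3–5 cohorts unobserved; 1000 runs.
- **III:** a further approximate check of the main contrasts.

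None is the cited data-augmentation program. Entries are ranges for I; II; III where available.

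| Quantity | Printed | Literal sentence | Only once 60 mg tried | Only if no dose acceptable |
|---|---|---|---|---|
| Scenario 1, none selected (%) | 6.5 | 72–82; 73–86; 60–65 | 16–36; 24–33 | 14–20; 12–27; 6–12 |
| Scenario 1, patients treated | 58.6 | 22–31; 22–31 | 47–54 (I) | 53–55; 46–58 |
| Scenario 2, none selected (%) | 14.7 | 41–51; 29–56; 40–44 | 23–37; 18–37 | 11–16; 12–22; 9–12 |
| Scenario 2, 80 mg selected (%) | 75.5 | 40–50 (I) | 48–70 (I) | 63–78 (I) |
| Scenario 4, patients at 150 mg | 22.2 | 0.5–1.9; 0.3–7; under 2 | 8–15 (I) | 10–15; 8–20 |

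The Monte Carlo standard error of the printed 6.5% is √(.065 × .935/1000) = 0.8 points, so simulation noise does not explain the literal-rule gap. In I, 32–44% of late-onset Scenario 2 runs under the literal rule stopped for low efficacy at 60 mg while a higher tried dose met both criteria. A single look at roughly the printed final allocations flagged 60 mg in at most 7% of Scenario 2 data sets, so that gap comes largely from early looks with few data.

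**Step 5: is an untried 60 mg evaluated?** Section 3.4 reports no patient starting at 60 mg, yet states: "The estimated EffTox desirability scores were 0.622, 0.787, 0.755, and 0.630 for the 60, 80, 120, and 150 mg doses". The model does return a value for an untried dose.

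**The case against.** The strongest reply is that the program, not the sentence, governed the trial. Section 14.1 delegates conduct to specialised software, which may well stop only when no dose is acceptable. The defect would then be one loosely worded sentence. This largely stands: that rule is the likely one, but the documents do not say so, and a reader cannot tell which rule the printed probabilities belong to.

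Second, the rule may presuppose that 60 mg has been tried. On that reading the Scenario 1 and 4 results overlap those of the no-acceptable-dose rule, and across simulators so do the Scenario 2 results (18–37% against 9–22%). No row cleanly excludes it. It is somewhat strained, because the table puts a mean of 3.5 and 3.2 patients at 60 mg in Scenarios 1 and 4 and the trial mostly continues.

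Third, the simulators are not calibrated. In I the fitted efficacy prior means were about .24/.29/.40/.46 against the stated .25/.30/.35/.50, and its no-acceptable-dose runs miss printed Scenario 1 (14–20% against 6.5%) and Scenario 4 (10–15 against 22.2). This limits precision, not direction: the literal rule lies much further from the printed rows.

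Fourth, the reported desirability scores are weak evidence. Even with efficacy 1, the Section 14.1 contour caps the score at 1 − pT/.65. At the reported toxicity rates that is 1 − (4/15)/.65 = .59 for 80 mg and 1 − (10/24)/.65 = .36 for 120 mg, against reported scores of 0.787 and 0.755. The scores are used here only to show that 60 mg was given a value, not that termination was judged on it.

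Finally, Section 3.4 reports enrolment through February 2020 and a preferred dose. Nothing there suggests that this rule ended the trial, although the reason for 42 rather than 60 patients is not given.

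**Conclusion.** The concern holds. As written, low efficacy at the lowest dose alone ends the trial, and no other text softens this. That conclusion needs no simulation: Scenario 2 shows a correct judgement on 60 mg discarding an acceptable 80 mg.

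The conflict with Section 14.2 is clear for the literal sentence. Across all simulations, Scenario 1 ends with no dose in 60–86% of trials against 6.5% printed, and Scenario 2 in 29–56% against 14.7%. Fewer than about 7 patients reach 150 mg in Scenario 4, against 22.2 printed. Stopping only when no dose is acceptable gives 6–27% and 9–22% in Scenarios 1 and 2, and about 8–20 patients at 150 mg in Scenario 4. These figures rest on assumed hyper-parameters and simplified handling of delayed outcomes, and the printed table has not been fully reproduced under any reading.

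The point concerns the stated rule and whether the stated operating characteristics belong to it. It does not show an error in the dose selection. It should be fixed, but is not critical.

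**What to change.** Establish from the program settings which termination rule was run in the trial and which was simulated for Section 14.2. Then align the text. Suggested wording: *The trial will be terminated and no dose level selected if no dose level satisfies both acceptability criteria; unacceptability of the lowest dose alone is a termination trigger only under the toxicity criterion.* State also whether a lowest dose that no patient has received is judged.

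Keep the separate toxicity trigger only if the program applies it, so that the correction does not create a new mismatch. In the immediate-outcome runs of simulator I, adding it changed the no-selection probability by at most 0.5 points. If Section 14.2 was simulated under a different rule, rerun and restate it.

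The cost is one sentence and a settings check, plus a rerun only if the check fails. No patients are needed.

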14.2 Design Operating Characteristics

Operating characteristics of the design are summarized below, based on simulations with 1000 replications per scenario. In the simulations, it is assumed that the times to toxicity and efficacy follow Weibull distributions, the percentage of toxicity (or efficacy) events occurring in the later half of each evaluation interval is 50%, and the accrual rate is 2 cohorts per month.

Scenario		Dose (mg/day)					
		60	80	120	150	None	
1							
	True pT, pE	.20, .25	.30, .45	.40, .70	.50, .95	-	
	Trade-off Value	-0.83	-0.58	-0.24	0.12	-	
	% selected	0	11.5	41.0	41.0	6.5	
	# Patients Treated	3.5	8.7	18.8	27.6	-	
2							
	True pT, pE	.20, .40	.30, .65	.60, .70	.90, .75	-	
	Trade-off Value	-0.53	-0.18	-0.55	-0.91	-	
	% selected	8.4	75.5	1.4	0	14.7	
	# Patients Treated	8.0	31.1	10.6	6.2	-	
3							
	True pT, pE	.30, .65	.60, .72	.65, .75	.70, .78	-	
	Trade-off Value	-0.18	-0.51	-0.52	-0.54	-	
	% selected	78.4	10.3	0.1	0	11.2	
	# Patients Treated	27.5	18.5	6.8	3.9	-	
4							
	True pT, pE	.10, .15	.15, .20	.20, .25	.25, .30	-	
	Trade-off Value	-0.87	-0.85	-0.83	-0.81	-	
	% selected	0	0	0	3.8	96.2	
	# Patients Treated	3.2	3.3	4.3	22.2	-	
5							
	True pT, pE	.50, .25	.60, .35	.70, .45	.80, .56	-	
	Trade-off Value	-1.30	-1.26	-1.21	-1.14	-	

% selected	0	0	0	0	100
# Patients Treated	4.2	6.2	4.9	5.4	-

14.3 Additional analyses

Demographics: For each treatment group (control, experimental), summary statistics will be provided for age, baseline disease status and prior treatments.

Toxicity: Adverse effects that will be evaluated include, but are not limited to infections, renal toxicity, hepatic toxicity, and pulmonary toxicity. Methods of assessment will include monitoring blood counts, and performing laboratory tests as indicated by clinical signs and symptoms. Evidence of toxicity or adverse events will be recorded at all clinic visits. All observed adverse effects will be graded for all patients and the degree of association of each with therapy assessed.

Quality of Life: Prior to inferential procedures, extensive descriptive analyses will be conducted for each of the measures obtained at each session. Descriptive statistics (e.g., means, ranges, standard deviations) will be computed, together with ninety-five percent confidence intervals for the means. Proportions of subjects falling outside normative ranges for the stress and QOL measures will also be calculated. Values for the standardized scales will be compared to normative data and patients receiving other types of cancer therapy. Graphical methods (e.g., boxplots and histograms) will be employed to more closely examine the distributions of the measures at each time point. Change scores for the stress and QOL measures will be computed as the simple differences between the baseline measure and subsequent evaluations. Bivariate associations between the raw scores, the change scores, optimism, social support, and demographic variables will be evaluated using Pearson's product moment correlation coefficients together with scatterplots where appropriate. These procedures will allow us to thoroughly characterize the stress and QOL profiles of this patient population across the sessions.

In this study, numerous models will be constructed to analyze the data and, therefore, the results will be treated as hypothesis generating and interpreted with caution. Inferential statistics will comprise paired t-tests of the stress and QOL measures. Significant test results ($p < .05$) will be interpreted as indicating significant changes in stress and QOL associated with the treatment. Linear regression analyses will then be used to construct prediction models using a composite stress and QOL score. In these analyses, the composite stress and QOL score will be regressed onto spirituality and social support at the start of the trial, and interaction terms will be calculated to determine whether these factors moderate stress and quality of life. Potential confounders include the stress and QOL measures obtained at baseline and demographic and treatment characteristics. Backwards step-wise regression will be employed to construct the final models, with a rejection criteria of $p > .05$. Multivariate methods, including repeated measures analyses, will be employed to further explore the potential changes in the stress and QOL measures over time. Standard residual based diagnostic procedures will be used to evaluate model assumption and normalizing transformation made as appropriate.

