6.5.1 Assessment Schedule

All patients will complete a full assessment battery at baseline, *prior* to treatment. Patients will then complete a brief assessment battery at week 2, week 4, week 6, and then every 12 weeks (see Table 4).

Table 4: Data collection sessions for psychosocial measures

BASELINE	FOLLOW-UP

 • FACT • SF-12 • Depression (CES-D) • Social Provisions Scale • History of depression • FMCS 	
 • FACT • SF-12 • CES-D • FMCS

Several measures used previously in our work on chronic stress and QOL will be used in the proposed study. In all cases, they have proven to be useful and sensitive measures of stress and QOL, have proven to be stable, reliable, and valid with groups of people who are and are not suffering from major depression or other psychiatric disorders. All surveys will be completed electronically using e-tablets and response data will be collected using the HIPAA-compliant Qualtrics software platform.

Quality of Life:

The Functional Assessment of Cancer Therapy (FACT) is a cancer-specific measure of *health-related quality of life*. This instrument was able to discriminate between individuals with metastatic and non-metastatic disease, as well as between patients at different stages of illness. The scale has been found to have good concurrent validity, high internal consistency (0.89), and good test re-test reliability (0.82 to 0.88). The FACT will be completed at each assessment.

General QOL – General QOL will be assessed using the Medical Outcomes Study 12-item short-form survey (SF-12). Responses are based on a Likert-type scale. The SF-12 is a health-related QOL measure that is responsive to minor versus major medical problems as well as psychiatric problems. It has good test-retest reliability (coefficients for various subscales range from 0.60 to 0.81) and good internal consistency (coefficients range from 0.78 to 0.93). The SF-12 will be completed at each assessment.

Proprietary of MD Anderson Cancer Center

Depression:

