- Optional: on the 4th week (\pm 3 days) of therapy on protocol (following at least 1 infusion of nivolumab): collect blood samples for immune testing and correlative studies to assess treatment response to combination therapy.

Proprietary of MD Anderson Cancer Center

10.4 Imaging scans (CT of chest and CT scan or MRI of abdomen/pelvis) will be performed to determine disease response at 6 weeks (42 days)(+/- 3 days), 12 weeks (84 days +/- 7 days), and every 12 weeks (84 days +/- 7 days), for as long as patients are receiving therapy on protocol. A follow-up CT or MRI of the brain will only be ordered if clinically indicated.

10.5 Echocardiogram will be obtained on the 12th week (\pm 14 days) of therapy on protocol and then repeat every 6 months (\pm 1 month) or as clinically indicated.

10.6 Complete e-tablet QOL assessments (FACT, SF-12, CES-D, FMCS) at 2 weeks (\pm 7 days), 6 weeks (\pm 7 days), 12 weeks (\pm 7 days) and every 12 weeks (\pm 7 days) thereafter.

10.7 End of Treatment Evaluation: Adverse events and tumor-related signs and symptoms will be assessed. For patients who develop toxicity related to study drug necessitating discontinuation of protocol therapy before restaging to assess tumor response, physicians treating these patients will make every effort to repeat the appropriate imaging studies if feasible and indicated to assess tumor response at the time the patients are taken off protocol treatment. For patients taken off protocol therapy due to disease progression, blood samples and tumor biopsy (optional at the physician's discretion) will be collected within 28 days from the time that disease progression is first confirmed and used for immune testing and correlative studies.

10.8 Long-term Follow-Up: Patients will be followed for survival every 3 months (90 days \pm 1 month or 28 days) by record review or telephone correspondence. Patients in long term follow up at the time of Long Term Extension Phase approval will be assessed for survival every 6 months (180 days +/- 1 month or 28 days)

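### QOL inference rests on paired t-tests that drop patients without the later score; if those who leave do worse, the tested change is too favourable, slightly early on and more from week 12

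*Combined protocol and SAP*

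**What the plan says.** Section 14.3 defines change this way: "Change scores for the stress and QOL measures will be computed as the simple differences between the baseline measure and subsequent evaluations". It then states: "Inferential statistics will comprise paired t-tests of the stress and QOL measures". A result with p below .05 "will be interpreted as indicating significant changes in stress and QOL associated with the treatment". The same paragraph adds that "the results will be treated as hypothesis generating and interpreted with caution", and it mentions repeated-measures analyses as further exploration, without naming a model. It gives no analysis set, missing-data assumption, dropout sensitivity analysis or multiplicity control for QOL.

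The forms are scheduled in two places:

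- Section 6.5.1 plans a "brief assessment battery at week 2, week 4, week 6, and then every 12 weeks".
- Section 10.6 reads "Complete e-tablet QOL assessments (FACT, SF-12, CES-D, FMCS) at 2 weeks", then weeks 6 and 12 and every 12 weeks. It omits week 4, as do the QOL row and footnote y of the study calendar.

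Section 10.6 sits under the evaluations during treatment. The calendar's QOL row has no end-of-treatment mark. Follow-up after treatment (Section 10.8) is for survival only, and Section 6.5 stops QOL in the extension phase. Section 12.0 says nothing new is collected after withdrawal.

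**The concern.** A simple difference exists only when both scores exist, so the t-test at any visit describes the patients who are still completing forms. In this trial leaving is not random. Section 3.4 reports 12 of 42 patients still on treatment at cutoff, 25 stopped for progression and 4 for adverse events. Taking those two categories as exclusive, 29 of the 30 patients off treatment left for reasons plausibly linked to worse QOL. Section 6.4 also takes patients off study for some persistent symptoms, such as prolonged severe fatigue, that QOL scales are likely to register.

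At stake is how the secondary QOL result is read. A mean change in stayers could be reported as the experience of all treated patients, and a p-value below .05 could reflect who remained rather than how patients changed. Week 12 deserves attention because Section 3.4 cites "higher quality of life, and higher hope for the future scores at 3 months" in comparing 80 and 120 mg.

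**Working it through.** The documents give no QOL sample size, power, SD or expected completion, so there is no planned figure to reproduce. The check is an illustration.

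**Inputs from Section 3.4.** 12/42 = 28.6% on treatment, 25/42 = 59.5% stopped for progression, 4/42 = 9.5% stopped for adverse events; all three agree with the text. Median PFS in this trial is 11.7 months.

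**Input from Section 3.2.3.2.** Median PFS on nivolumab in CheckMate 025 is 4.6 months, the proxy available at the design stage.

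**Assumptions.**
- QOL is observed only on treatment, and treatment stops at progression.
- PFS is exponential.
- Scores are oriented so that higher is better. Standardised change has mean 0 and SD 1 in all 42 patients.
- Change has correlation ρ of 0.3 to 0.5 with the latent variable that decides who stays.
- Tests are two-sided (Section 14.3 does not say).

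**Formulas.**
- Share on treatment: S = 0.5^(months / median PFS), with months = weeks / 4.345.
- Bias in the completer mean: ρλ, where λ = φ(z)/S and z is the (1 − S) normal quantile.
- SD among completers: √(1 − ρ²λ(λ − z)).
- Rejection rate: noncentral t with n = 42S (rounded) and noncentrality bias/SD × √n.

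**Week 12 worked through, 11.7-month median.** 12/4.345 = 2.76 months, so S = 0.5^(2.76/11.7) = 0.849 and n = 36. Then z = −1.03, φ(z) = 0.234 and λ = 0.234/0.849 = 0.276. The bias is 0.3 × 0.276 = 0.08 to 0.5 × 0.276 = 0.14 SD. The test rejects 8% to 14% of the time instead of 5%.

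| Median PFS | Week | On treatment | n | Bias (SD), ρ 0.3–0.5 | Rejection of nominal 5% test |
|---|---|---|---|---|---|
| 11.7 mo | 6 | 92% | 39 | 0.05–0.08 | 6–8% |
| 11.7 mo | 12 | 85% | 36 | 0.08–0.14 | 8–14% |
| 11.7 mo | 24 | 72% | 30 | 0.14–0.23 | 12–26% |
| 11.7 mo | 48 | 52% | 22 | 0.23–0.38 | 19–46% |
| 4.6 mo | 12 | 66% | 28 | 0.17–0.28 | 14–33% |
| 4.6 mo | 24 | 44% | 18 | 0.27–0.45 | 20–51% |

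**Cross-check by a simple mixture.** Bias = (1 − S) × (mean change in stayers − mean change in leavers). With S = 0.849 and a gap of 0.5 to 1.0 SD, this gives 0.151 × 0.5 = 0.08 to 0.151 × 1.0 = 0.15 SD, in line with the week-12 row.

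**Multiplicity, a separate point.** Four follow-up scales at the three visits through week 12 in Section 10.6 give 12 tests. If they were independent, the family-wise error would be 1 − 0.95^12 = 46%. Positive correlation among scales and visits lowers it.

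**Visit lists.** Week 4 appears only in Section 6.5.1. In that section the 12-week interval could run from day 1 (which includes week 12) or from week 6 (which does not).

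**The case against.** The strongest reply is that QOL is secondary, plays no part in the Lo-EffTox rule, is labelled exploratory, and already has repeated-measures analyses planned. That justifies a modest grade. It does not remove the point: a caution about interpretation leaves the bias where it is, the significance reading is attached to the paired tests, and the repeated-measures work has no stated model or missing-data assumption.

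Other objections stand in part:

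- On-treatment collection is inferred from the section title and the calendar. Sections 10.3 and 10.4 limit themselves to patients on therapy; 10.6 does not say so.
- Section 8.3 allows treatment beyond progression, which would raise retention and shrink the figures above. Stopping for adverse events before progression works the other way.
- The direction depends on leavers doing worse, which the documents make plausible but do not show.
- A likelihood model is valid only if dropout is explained by observed data. Progression and toxicity need not be reflected in earlier QOL scores, so the model alone may not cure the bias.

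A reader might also infer that these t-tests drove the choice of 120 mg. The documents do not support that. Section 3.4 compares doses by posterior probabilities, alongside ORR and PFS; a before–after t-test compares no doses; and nothing shows that dropout differed by dose. Nor does Section 14.3 claim a causal effect: it speaks of association.

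**Conclusion.** The point holds as an improvement that should be made to a secondary analysis. The planned test describes stayers, leaving is tied to outcomes likely to worsen QOL, and no handling of missing scores is specified. At the trial's own median PFS the bias is small at week 6, about 0.08–0.14 SD at week 12, and material only later (0.23–0.38 SD at week 48). At the historical 4.6-month PFS the week-12 figure would be 0.17–0.28 SD. These sizes rest on an assumed ρ of 0.3–0.5, exponential PFS as a proxy for form completion, and zero true change.

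Two further readings go too far. A large distortion at week 12 does not follow when about 85% are expected to remain on treatment. Week 12 is ambiguous in Section 6.5.1 rather than plainly absent; only the week-4 mismatch is clear.

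**What to change.** - Make a likelihood-based repeated-measures model the main QOL analysis: all patients with a baseline score, visit as a category, and baseline score and starting dose as covariates. Report estimates with intervals.
- Keep the paired t-tests as descriptive.
- Because the model assumes missing at random, add a sensitivity analysis for dropout due to progression, death or toxicity.
- Report completion and reasons for missing forms by visit and starting dose.
- If p-values are quoted, either state that 12 tests through week 12 carry a family-wise error of up to about 46% if independent, or apply a false-discovery adjustment.
- Reconcile Sections 6.5.1 and 10.6 on week 4, and say from which day the 12-week interval in 6.5.1 is counted.

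The cost is SAP wording and a little more programming on data already collected. The downside is that the QOL estimates may look less favourable.
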